We will recruit 280 participants; 70 in each of the four arms. Wiberg-Itzel et al [2] observed mean umbilical artery pH 7.23 (SD 0.07) in the non-intervention group. With our sample size, we will have 80% power (significance level 0.05) to detect mean pH changes of 0.04 and above in each arm. We are interested in detecting an effect size of 0.2 and above, which we deem to be a moderate effect size. The total sample size needed to detect a between-factor mean effect size of 0.2, by repeated measures analysis of variance (ANOVA) with a type 1 error margin of 5%, across 4 groups with 5 repeated measurements; was 224 at a power of 91%. Assuming a 20% loss to follow up in our study; we will need 280 participants (70 in each of the 4 groups). The sample size was calculated using G* Power software version 3.1 using the test family for the F test, and the statistical test for ANOVA repeated measures, between factor analysis & within-between interaction [10]. Therefore, our sample size will also be sufficient to detect a within and between-subject interaction (intervention and time interaction) with a power of 99%. To obtain these estimates, we will construct an interaction term between the intervention and the time variable. We are confident that we shall be able to accrue this number of participants in a period of six calendar months, on the basis of our experience working in the same hospital [7]. In order to detect a change in maternal pH, a minimum of two measurements are needed from a participant. However, with improvement of obstetric care, many women deliver within 30 minutes of taking the baseline measurements and hence no second measurement is obtained. To account for this form of right censoring, we have inflated our sample size by 192 participants to ensure that we have at least 280 women with at least two pH measurements. We will recruit 472 participants; 118 in each of the four arms.

Outcome variables

The primary outcome measure will be the mean change in maternal pH from baseline in each group. The secondary outcomes will include, mean pH and lactate in maternal and umbilical blood, early neonatal death, safety (side effects) of sodium bicarbonate, primary PPH, sepsis and death. Furthermore, the plasma concentrations of HCO₃ levels will be measured as well to accurately estimate the required dose.

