Randomisation: A sequence of random numbers will be generated by an independent biostatistician using an online randomization service at www.sealedenvelope.com in permuted block sizes of four, six and eight. An independent, off-site pharmacist will prepare and consecutively number identical study packages using

the generated random numbers. This will ensure that the allocation is concealed. At the study site, after gaining consent, the research midwife will take the next sequentially labeled study drug package and administer its contents to the eligible participant. Therefore, both the participants and data collectors will remain blinded throughout the study.

Intervention/ Comparator: Eligible participants will be randomly assigned to receive 100 mls (8.4g), 150 mls (12.6g) and 200 mls (16.8g) of 8.4% sodium bicarbonate solution, or placebo (50 mls of NS 0.9%) in a ratio of 1:1:1:1. The study drug (Sodium Bicarbonate 8.4% and Normal Saline 0.9%) will be contained in identical 25 mL glass vials (Neon Laboratories Ltd, Mumbai, India), administered intravenously as a single bolus dose. Since the average waiting time for CS in our labour ward is approximately 110 minutes [11], there will be no need for a repeat dose.

In addition, all patients will receive the available Ministry of Health recommended standard preoperative care for all patients with OL which includes antibiotic prophylaxis, intravenous fluid replacement (1.5 L of normal saline), bladder drainage and lying in left-lateral position as they are being prepared for caesarean section [23]. Details in flow diagram 1.

Data collection

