Data analysis plan

Data will be analyzed using Stata version 17.0 (StataCorp; College Station, TX, USA). We will describe categorical variables as proportions and compare them with chi-squared tests or Fischer's exact tests as appropriate. We will describe continuous variables as means (SD) OR medians (IQR) and compare them with t tests or Mann-Whitney U tests as appropriate. Our analysis will be by intention to treat. To determine the safety of sodium bicarbonate infusion, we will compare the incidence of side effects in each arm and report risk differences.

For the primary outcome of acidosis (pH and lactate) between-subjects repeated measures ANOVA will be conducted. We will also conduct within-subject interaction repeated measures ANOVA to assess for differences in the rate of change of pH between the groups.

We will use histograms, P-P plots, k-density, and Q-Q to assess the distribution of normality of continuous outcomes. In case the distribution of normality is not met; we shall transform our data and this decision will be guided by Stata's *gladder* command that shows various transformation options.

All analyses will be followed by a Bonferroni posthoc test for multiple comparisons, a Friedman test to compare rates of change between the various groups, and a Mauchly's test of Sphericity to check for equal variance among the combinations of the various groups. We will use Margins and Margins plots to obtain marginal means and graphical descriptions of the interaction between various groups and time.

Data Monitoring

Independent Data Monitoring Committee (IDMC)

An independent data monitoring committee (IDMC) will be appointed consisting of 3 members: a statistician, an obstetrician/gynaecologist, and a paediatrician. They will operate according to the IDMC charter, which will be developed with the members. IDMC will be encouraged to follow the recommendations of the international DAMOCLES group for IDMC activities.[12] The IDMC will monitor the trial once with a focus on issues relating to the quality of trial conduct, such as overall and site-specific rates of recruitment, adherence to trial interventions, visit schedules, losses to follow-up, and administrative and safety data. It will review administrative and safety data approximately every three months. The treatment groups will be masked in the IDMC reports.

Interim analyses and stopping guidelines

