Interim analyses: The interim analysis of efficacy data will be performed by the IDMC statistician. One analysis will be conducted according to the group sequential design when 50% of the inclusions are recorded. According to the O'Brien-Fleming alpha spending function, using a group sequential design and assuming a power of 80% and a significance level of 5%, the first interim analysis includes 140 subjects and has an information rate of 50%, efficacy bounds of -2.96 and 2.96, and p-value 0.003 (figure 3). These calculations were made using the RPACT RShiny app (<https://rpact.shinyapps.io/public/>). Interim trial data will be kept confidential and restricted to the IDMC, except if early stopping of the trial is recommended.

[figure not shown]

Figure 3: Figure showing efficacy bounds (critical value) at the interim analyses (50% accrual rate) and how these will change as the study progresses

Stopping guidelines

1. We propose the following stopping rule: “a statistically significant difference ($p \leq 0.003$) at the interim analysis according to the O'Brien-Fleming spending function for group sequential design) in the primary outcome between the treatment arms.
2. SAEs will be continuously monitored during data entry and reported to the IDMC. Any imbalance between expected occurrence and actual occurrence will be assessed by the IDMC statistician when 50% inclusions are recorded, and discussed with the IDMC.
3. The IDMC will provide a recommendation to stop or alter the design or conduct of the trial in case of high efficacy and/or poor adherence or unacceptable side effects that can be ascribed to the intervention according to pre-determined stopping rules and criteria. While the reviews of safety will consider both expected or unexpected adverse events, and the relative rates of death.
4. If the IDMC recommends stopping the trial early, a meeting of the principal investigator, the trial sponsor, the trial steering committee and the IDMC will be held to decide on the trial discontinuation. In case of disagreement, the advice of independent external experts will be sought. A report will be submitted to the Local IRB (BUIRB) as soon as possible and not later than 14 days after the decision.

Ethics and consent process

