We plan to conduct one interim analysis, when half (25%) of the participants have been recruited. This will be undertaken by the independent data monitoring committee (IDMC) composed of an obstetrician, a paediatrician and a statistician with research experience. These will be appointed by the sponsor of the study, Busitema University. The stopping rules agreed upon in the terms of reference for the IDMC will be based on: safety concerns, outstanding benefit, and futility. The IDMC will have the mandate to halt the study if the occurrence of adverse events (Safety) in any of the intervention arms is greater or equal to 10% in comparison to the placebo arm. All the serious adverse events (SAE's) will be reported and closely followed, until resolution following the existing statutory guidelines. However, this is unlikely to happen because the active drug (sodium bicarbonate) has a very good safety profile in both clinical use and research even among pregnant women in children. Furthermore, we will ensure that our study protocol is approved by both the Busitema University Faculty of Health Sciences Research and Ethics committee (BUFHS), and the Uganda National Council for Science and Technology (UNCST).

Quality control: All our research assistants will be qualified midwives/nurses, with training in good clinical practice (GCP). They will also receive training in the study protocol procedures during the trial dry run phase and at regular intervals throughout the implementation of the trial. The electronic questionnaire will be coded with checks and skips to ensure internal consistency. All the required blood tests will be done at the bedside using the RAPIDPoint® 500e Blood Gas System (Siemens Healthcare GmbH)[16]. Our choice of this system was informed by its ability to measure a range of parameters, using only 100 microliters of blood. Additionally, women with obstructed labour requiring urgent intervention, hence the need for a

BUFHS-2024-164_Protocol_SoBicOL-II Study_V1.3_10 September 2025_Page 14 of 25

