short turnaround time on blood results to inform clinical decision making. In the event of system downtime, we will use a YSTE-BG100 Blood Gas Analyzer (Yuesen Med, China) as a backup. The YSTE-BG100 is a compact and user-friendly device that can rapidly assess key parameters including pH, lactate, glucose, electrolytes, and blood gases [17], thereby ensuring continuity of care even when the RAPIDPoint® 500e Blood Gas System is down. In our previous trial the study drug was sourced from the local supplier accredited by the National Drug Authority (NDA). We intend to use 8.4% sodium bicarbonate (intervention), and sodium chloride 0.9% (placebo) from NEON laboratories Ltd, Mumbai, India.

Adverse events/side effects: Based on the package insert labelling for sodium bicarbonate and a review of the literature [18], we will actively monitor for the following; increased thirst, continuing loss of appetite, swelling of the lower limbs, venous irritation, muscle pain or twitching, continuing headache, nausea or vomiting, stomach cramps, unusual tiredness or weakness, nervousness or restlessness, mood or mental changes, frequent urge to urinate, slow breathing and cellulitis at the injection site. This will be done hourly for the first six hours, six hourly for the next 18 hours and then daily throughout the period of hospitalization.

Follow-on plan

We plan to publish our results in a peer reviewed journal irrespective of the findings, as we have demonstrated in the past. Furthermore, we have established contact with [name] in Oslo to advise on the setup of our current study. His group is undertaking similar work (<https://ichgcp.net/clinical-trials-registry/NCT05719467>), and they could be potential collaborators on a larger grant application if the results are positive (see attached support letter). We have a community advisory group that is crucial in disseminating our findings to the lay public. [name] is also a member of National Safe Motherhood Executive Committee (NASMEC), a ministry of health technical advisory group on maternal health. He will disseminate the findings in this group.

Table 2: Proposed study timelines

Activity	2024												2025					
	Jan	Feb	Mar	Apr	May	Jun	Jul	Aug	Sep	Oct	Nov	Dec	Jan	Feb	Mar	Apr	May	Jun
REC & UNCST approvals	*	*	*	*	*													
Recruitment of staff					*	*	*											
Procurements		*	*	*	*	*	*	*	*	*	*							
Data collection							*	*	*	*	*	*	*	*	*	*	*	*
Data analysis											*	*	*	*	*	*	*	*

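### The 10% adverse event margin for halting the trial is undefined and makes no allowance for chance, and no planned safety comparison uses the blood chemistry that Table 1 collects

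*Combined protocol and SAP*

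**What the plan says.** All references are to the combined protocol and SAP.

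- **Independent Data Monitoring Committee (under Management).** The IDMC may halt the study if adverse events "in any of the intervention arms is greater or equal to 10% in comparison to the placebo arm". This is the only numeric safety criterion in the document. The same paragraph places the single interim at half of recruitment but gives 25% in brackets.
- **Interim analyses and stopping guidelines.** The interim is at 50% of inclusions, with 140 subjects. The IDMC may recommend stopping for "unacceptable side effects that can be ascribed to the intervention according to pre-determined stopping rules and criteria". Serious adverse events, unexpected events and deaths are also considered, without thresholds. A recommendation to stop goes to a joint meeting for decision.
- **Data Monitoring.** Safety data are reviewed about every three months, and "The treatment groups will be masked in the IDMC reports".
- **Sample size estimation and sampling.** "We will recruit 472 participants; 118 in each of the four arms".
- **Data analysis plan.** For safety, "we will compare the incidence of side effects in each arm and report risk differences".
- **Adverse events/side effects, and Appendix 1, part I.** The monitored items are symptoms and local signs, beginning with "increased thirst, continuing loss of appetite, swelling of the lower limbs, venous irritation".
- **Table 1.** Blood gases including pH, electrolytes including sodium, potassium and calcium, and plasma bicarbonate are measured at baseline, every 30 minutes to 150 minutes, and at birth.
- **Exclusion Criteria.** Baseline hypokalaemia and alkalosis are excluded because they raise the risk of adverse reactions.

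**The concern.** A raw margin on the worst of three arms, each compared with the same small placebo group, will sometimes be met by chance. The efficacy rule has a boundary with known error. The safety rule has none, and its scale, event and timing are left open, so two IDMC members could apply it to the same table and disagree. A committee given a mandate by such a margin cannot tell how much evidence the signal carries.

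The second part concerns specific objective 2, safety. The planned comparison is of side effects. A shift in electrolytes or acid-base state without symptoms would appear in no planned safety table, although the values are collected and the eligibility criteria treat such disturbances at baseline as a hazard.

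**Working it through.** **The plan's own interim figure.** An O'Brien-Fleming-type spending function at 50% information, with two-sided 5% significance, spends 2 × [1 − Φ(2.2414/√0.5)] = 0.00153 per side. That gives z = 2.963 and two-sided p = 0.00305, matching the stated 2.96 and 0.003. The 140 subjects are 50% of 280, not of the current 472. No operating figure is given for the safety rule, so there is none to reproduce.

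**Inputs from the document.** Three active arms share one placebo arm ("or placebo (50 mls of NS 0.9%) in a ratio of 1:1:1:1"). The document supports three interim sizes:
- 140/4 = 35 per arm
- 50% of 472 = 236, or 59 per arm
- 25% of 472 = 118, or about 29 per arm

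**Assumptions.** Women with at least one counted event are binomial, with the same true risk p in all four arms. The document gives no p, so 5% to 50% is shown.

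**Percentage-point reading.** An arm meets the margin if its count exceeds the placebo count x by at least m = 0.1n, rounded up. That is 3 women at n = 29, 4 at n = 35 and 6 at n = 59. With F the binomial distribution function,

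P(at least one arm meets it) = Σₓ Bin(x; n, p) × [1 − F(x + m − 1)³].

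| Women per arm | p = 5% | 10% | 20% | 30% | 50% |
|---|---|---|---|---|---|
| 35 (stated 140) | 8% | 19% | 31% | 36% | 39% |
| 59 (half of 472) | 3% | 12% | 23% | 29% | 32% |
| 29 (25% of 472) | 16% | 30% | 41% | 45% | 47% |

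**Relative reading.** If an arm needs only 1.1 times the placebo count (one event suffices when placebo has none), the chance at 35 per arm is 68%, 69%, 63% and 60% at p = 10%, 20%, 30% and 50%.

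**Real harm.** If one arm truly carries a 10-point excess, that arm meets the percentage-point margin with probability Σₓ Bin(x; n, p) × [1 − F(x + m − 1; n, p + 0.1)]. This is 49% to 56% for n from 29 to 59 and placebo risks of 5% to 30%, so the rule is close to a coin toss on the excess it names.

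**Repeated looks, only if the rule applied at each review.** With four assumed looks at 30, 59, 89 and 118 per arm, the chance with no harm is about 18%, 34%, 48% and 54% at p = 5%, 10%, 20% and 30%.

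**Chemistry, section against section.** Table 1 collects the values. The exclusion criteria treat baseline disturbance as a reaction risk. The monitored list, the side-effect form, the safety paragraph of the analysis plan and the stopping guidelines name none of them.

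**The case against.** - **One in three.** A reader might infer that a harmless trial meets the rule about one time in three. The document does not fix that figure. It needs an event risk of roughly 20% to 30%, the percentage-point reading and the 140-woman look. At a 5% risk the figure is 8%, and at 59 per arm about 32% is the ceiling. Mild symptoms may well be common in labour, but that is an assumption.
- **Not a false halt.** A mandate is a power. The stopping guidelines ask whether side effects can be attributed to the intervention and send any stop recommendation to a joint meeting. This stands: the table gives the chance of meeting the margin, not of stopping. The charter might also define more, but it is still to be developed.
- **Chemistry is not shut out.** One might infer that a biochemical harm could never count. The rule does not limit adverse events to the symptom list, and serious or unexpected events reach the IDMC. pH is the primary outcome, and bicarbonate is modelled for pharmacokinetics. The gap is therefore narrower: no named limits, and no planned safety comparison by arm.
- **A bare 10% incidence.** Reading the rule as any arm reaching 10% ignores its reference to placebo and is not supported.
- **Masking.** Masked reports may mean coded groups, and the IDMC statistician does run the interim comparison. Lack of access to the codes is not stated. It simply needs settling.
- **Repeated looks.** The rule is described beside a single interim, so its use at every three-monthly review is not established.
- **A sensitive harm trigger may be deliberate.** This is fair. Also requiring a one-sided 98.3% confidence limit (5% shared over three arms) to exclude zero would, at 35 per arm and 20% placebo risk, cut the chance that any arm meets the rule under a true 10-point excess in one arm from 56% to 14%. That trade belongs to the sponsor and the IDMC.

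**Conclusion.** The concern holds in two limited parts.

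1. The 10% rule lacks a scale, an event definition, a look and any allowance for three comparisons. How often chance alone meets it depends on an event risk the document does not state: from 3% to 47% over the three possible interim sizes and risks of 5% to 50% on the percentage-point reading, and higher on the relative reading. These figures assume independent binomial counts, equal risk in all arms and a single look. The margin is weak evidence for harm when met and weak reassurance when not met.
2. Safety is to be judged on side effects, while the chemistry already collected enters no planned safety comparison. This part rests on the text alone and needs no assumed rate.

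Neither part shows that the trial would be wrongly halted or that the IDMC could not act on a biochemical harm.

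**What to change.** 1. Reconcile the Data Monitoring, stopping guidelines and Management sections into one safety rule. The sponsor states its 10% as an absolute risk difference in named events, counted per woman, at a stated look. It serves as a trigger for IDMC review, with arm identity available to the IDMC statistician. Report the chance that it is met with no harm and with real harm over a range of event rates. Any halt criterion stays with the sponsor and the IDMC.
2. Add to the safety analysis, by arm, summaries and out-of-range proportions for the pH, sodium, potassium, calcium and bicarbonate values in Table 1, with limits set by the clinical team. Include them in the IDMC reports.

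The cost is protocol and charter wording, a short calculation and one more safety table. No new samples are needed.

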Our research assistants will be qualified midwives with training in data collection, using dedicated password protected android devices. We will also review relevant health facility records such as antenatal care cards, case notes/file, the maternity and theatre registers. Laboratory parameters including lactate will be measured at baseline, and every thirty minutes after study drug administration until delivery to obtain samples for lactate measurement in umbilical cord blood and the myometrium. The participants will be followed for 7 days postnatal to ascertain the secondary perinatal outcomes and for 14 days postpartum to determine the secondary maternal outcomes. In the first 24 hours after study drug administration, the participants will be closely monitored to identify any drug reactions/adverse events. After administration of the study drug, all the participants will be actively monitored by a research midwife up to 24 hours. The women will be examined and asked directly about the presence of side effects.

Sample collection quality control

Qualified and well-trained research midwives will draw five millilitres (ml) of blood by venipuncture at the antecubital fossa of the non- dominant arm from each participant using a five millilitres syringe. After removing the epidermal needle and the tops of the vacutainers, two millilitres will be emptied into a purple top vacutainer for a full blood count, blood grouping and cross-matching as part of the standard preoperative preparation for all patients with obstructed labour in the hospital. The remaining three millilitres will be emptied into a red top vacutainer for blood chemistries including electrolytes, these are not part of the routine preoperative preparation for patients before caesarean section. Each blood sample will be transported to the laboratory in an ice-cooled container within 30 minutes of collection. Urine samples: Mid-stream urine, ten millimeters will be collected in sterile urine container from the mothers. We will monitor strict adherence to the standard operating procedures for collecting and handling participant samples through ongoing training and spot checks.

Cord blood collection

After the baby is born, the midwife will double clamp and cut the umbilical cord. Cleanse a 4" - 6" area of the umbilical cord with alcohol to remove maternal blood and contaminants (before the delivery of the placenta, if possible). Then blood will be drawn from the cord with a needle.

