3. BMI
4. Cardiovascular system
 - i. BP
 - ii. Pulse
 - iii. SPO2
5. Respiratory system
 - i. Respiratory rate
6. Abdominal examination
 - i. Does the participant have a visible Bandl's ring?
 - ii. Doe the participant have palpable uterine contractions?
 - iii. What is fetal heart rate?
7. Vaginal examination
 - i. Is the vulva and vagina oedematous?
 - ii. Is the caput present?
 - iii. Is the pelvis adequate?
 - iv. Have the membranes ruptured?
 - v. What is the colour of the liquor?

D. Baseline laboratory test results - Maternal

Parameter	Blood	Amniotic fluid	Urine
pH		Not Applicable	Not applicable
Blood gasses		Not Applicable	Not applicable
Lactate			

E. Study drug administration

Time	
Package number	

F. Maternal outcomes after study drug administration

Time (minutes)	Lactate in maternal blood sample	Lactate in amniotic fluid sample	Maternal arterial blood gasses	Maternal pH
0				
30				
60				
90				
120				
150				

G. Maternal outcomes at birth

1. Mode of delivery
 - i. SVD
 - ii. CS
2. For all those that delivered by CS, record the myometrial lactate here
3. What was the duration of labour?
4. Measured blood loss at birth
5. How well did the uterus contract after birth? (scale 1-10)
6. Assistant at delivery?
 - i. Midwife
 - ii. Specialist
 - iii. Medical Officer
 - iv. Intern
 - v. Student
 - vi. Others
7. Did the participant sustain any injuries in the birth canal?
 - i. Yes
 - ii. No

H. Newborn outcomes at birth

1. Record the Agar score here
 - i. At one minute
 - ii. At five minutes
2. Record the birth weight here
3. Lactate in arterial cord blood
4. Lactate in venous cord blood

Within one minute of child birth	Lactate in maternal blood sample	Lactate in amniotic fluid sample	Maternal arterial blood gasses	Maternal pH
Arterial cord blood				
Venous cord blood				

I. Monitoring of side effects and adverse events for 24 hours period after administration of study drug

(Tick all that apply)

1. Frequent urge to urinate		10. Swelling of feet or lower legs	
2. Headache (continuing)		11. Unpleasant taste	
3. Loss of appetite (continuing)		12. Increased thirst	
4. Mood or mental changes		13. Unusual tiredness or weakness	
5. Muscle pain or twitching		14. Venous irritation	
6. Nausea or vomiting		15. Cellulitis	
7. Stomach cramps		16. IV site pain	
8. Nervousness or restlessness			
9. Slow breathing			

J. Follow up outcomes

1. Perinatal outcomes on the 7th day postnatal
 - i. Alive and well
 - ii. Alive and not well
 - iii. Dead

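### Side-effect list and monitoring window differ between the text and the form, and non-serious events after 24 hours have no itemised, dated entry

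*Combined protocol and SAP*

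**What the plan says.** **Item list.** The Adverse events/side effects section opens its list with "we will actively monitor for the following; increased thirst, continuing loss of appetite, swelling of the lower limbs, venous irritation, muscle pain or twitching" and closes it with "mood or mental changes, frequent urge to urinate, slow breathing and cellulitis at the injection site". Counted through, it has 14 items. Appendix 1 section I is a tick list of 16 items, ending with "16. IV site pain".

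**Window.** The same section sets hourly checks for six hours and six-hourly checks for the next 18 hours, "and then daily throughout the period of hospitalization". Data collection says: "In the first 24 hours after study drug administration, the participants will be closely monitored to identify any drug reactions/adverse events". Study procedures also gives 24 hours for active monitoring by the research midwife. The form heading reads: "I. Monitoring of side effects and adverse events for 24 hours period after administration of study drug".

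**Use of the data.** Safety is specific objective 2. The Data analysis plan compares side-effect incidence between arms by risk difference and names neither items nor window. The Independent Data Monitoring Committee section lets the committee halt the study "if the occurrence of adverse events (Safety) in any of the intervention arms is greater or equal to 10"% in comparison with placebo. It does not say which events count or over what period.

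**The concern.** The protocol text gives two windows, and the form follows the shorter one. The form also records two items that the text does not list. An analyst working from the text would look for daily records up to discharge and find no itemised field for them. An analyst working from the form would count events to 24 hours on a longer list.

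The window matters more. The text already commits staff to daily ward checks, but the result of a check on day 2 or later has no line on the form by item and date. Injection-site cellulitis and leg swelling are on both lists and could first appear after 24 hours. If such events are missed, the risk differences for a stated objective describe the first day only, although the text says otherwise. Dates of non-serious events may not be recoverable after discharge.

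**Working it through.** **1. Compare the lists.** Text, 14 items: thirst, loss of appetite, lower-limb swelling, venous irritation, muscle pain or twitching, headache, nausea or vomiting, stomach cramps, tiredness or weakness, nervousness or restlessness, mood or mental changes, urge to urinate, slow breathing, cellulitis. Form section I, 16 items: all 14 of these, plus unpleasant taste and IV site pain. No item is in the text only.

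**2. Compare the windows.**

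| Place | End of side-effect monitoring |
|---|---|
| Study procedures | 24 hours |
| Data collection | 24 hours |
| Appendix 1 section I | 24 hours |
| Adverse events/side effects | end of hospital stay |

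The split is not simply text against form: two text sections agree with the form and one does not.

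**3. Look for another place to record late events.** Section J has a three-way maternal status and a free-text reason. Serious adverse events are reported separately and followed to resolution. Neither gives an itemised, dated entry for a non-serious event.

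**4. Effect of the window on one item.** The documents give no rates, so the inputs here and in step 5 are assumptions. Let D be the true risk difference, s the share of cases starting after 24 hours, and c the share of those late cases recovered by other routes, with s and c equal in all arms.

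Recorded difference = D × [1 − s × (1 − c)]

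With D = 10 points and c = 0 (nothing recovered, the worst case):
- s = 25%: 10 × 0.75 = 7.5 points
- s = 50%: 10 × 0.50 = 5 points
- s = 75%: 10 × 0.25 = 2.5 points

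With s = 50% and c = 50%: 10 × (1 − 0.25) = 7.5 points. If no cases start late, nothing is lost.

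**5. Effect on an any-event comparison, if one were used.** The plan defines no such composite. If base risk is b and additional events occur independently with probability e among those event-free, the combined risk is 1 − (1 − b)(1 − e).

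*Two extra items,* base 20% placebo and 25% active (difference 5.0 points):
- Extras 2% v 10%: (1 − 0.75 × 0.90) − (1 − 0.80 × 0.98) = 0.325 − 0.216 = 10.9 points
- Extras 2% v 2%: 0.265 − 0.216 = 4.9 points

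*Late first events,* 24-hour rates 20% and 28% (difference 8.0 points):
- Late 5% v 10%: (1 − 0.72 × 0.90) − (1 − 0.80 × 0.95) = 0.352 − 0.240 = 11.2 points
- Late 5% v 5%: 0.316 − 0.240 = 7.6 points
- Late 15% v 5%: 0.316 − 0.320 = −0.4 points

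The difference hardly moves when the added events are equally frequent in the arms. It can move either way when they are not.

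**The case against.** The strongest reply is that little follows from the mismatch. The Data analysis plan can be read as item-by-item reporting. On that reading the two extra form items add two rows and leave every other risk difference unchanged. This stands. The list mismatch alters a total only if an any-event comparison is made.

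A reader might infer that the 10% halt rule turns on which list is used. The documents do not support that. The rule speaks of adverse events, not of either list. The Stopping guidelines have safety reviews consider expected and unexpected events and relative rates of death, and a recommendation to stop goes to a joint meeting. It is also unclear whether 10% is absolute or relative. Any probability of crossing it would rest on assumed arm differences in the extra items, and the documents give no rates for these. The new items may also overlap with venous irritation, which is already on both lists.

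A reader might also infer that the form cannot hold late events at all. That is too strong. Section J takes free text, serious events are reported separately, and Study procedures mentions an electronic questionnaire collecting clinical information in hospital up to 14 days postpartum. What stands is narrower: Appendix 1 has no itemised, dated entry for a non-serious side effect after 24 hours, so its capture depends on what someone writes under a general status question.

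**Conclusion.** The point holds as an inconsistency in what safety data are captured. The text has 14 items and the form 16; one section runs to discharge and three places stop at 24 hours; nothing in the documents resolves either difference. The practical consequence is possible under-counting of non-serious events first seen in the planned daily checks, and so risk differences for specific objective 2 that do not match the stated monitoring.

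The size cannot be computed. The figures in the working are illustrations under assumed rates, independence, and (in step 4) equal late shares and recovery across arms. They show what the effect depends on, not what to expect. It would be wrong to conclude that safety is biased by a known amount or in a known direction, or that the trial is more likely to be halted. The correction is worth making because it is nearly free and late event dates may be hard to recover afterwards.

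**What to change.** - Reconcile Study procedures, Data collection, Adverse events/side effects and Appendix 1 section I to one item list and one window. State explicitly whether unpleasant taste and IV site pain are on the list.
- Because daily checks are already planned, give section I dated entries by item through discharge. Dated entries also allow a 24-hour count from the same data.
- In the Data analysis plan, report risk differences by item on that list and window.
- Have the Data analysis plan and the halt rule in the Independent Data Monitoring Committee section refer to the same definition. Which events count toward the halt rule is for the sponsor and the committee to state.

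The cost is wording, a slightly longer form and minor additional data entry; no new checks are needed.
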